9.1.2 Bone marrow infiltration

Will be assessed on sagittal T1 and T2 weighted MRI views of the lumbar spine and coronal T1 and T2 weighted MRI views of the entire bilateral femurs. A categorical bone marrow infiltration score will be calculated based on the amount of fat in the basivertebral vein region and the T1 and the T2 signals (18).

Bone marrow infiltration will be measured at screening and then yearly.

Bone MRI will be read locally and centrally. The central reads will be used for analysis.

9.1.3 Bone mineral density (BMD)

Will be measured by DXA of both hips and the lumbar spine. T and Z scores, and bone mineral densities will be provided by the DXA report.

Bone mineral density will be measured at screening and then yearly.

9.1.4 Lytic lesions, osteonecrosis, fractures and infarcts

Lytic lesions, osteonecrosis, infarcts and fractures will be assessed on bone MRI and bone X-Ray.

9.1.5 Bone biomarkers

Will include

- Total procollagen type 1 N-terminal propeptide (P1NP), a marker of bone formation
- C-terminal telopeptide of type 1 collagen (CTX), a marker of bone resorption
- MIP 1 β

These biomarkers will be measured at baseline and then every 6 months.

These markers will be measured by a central laboratory.

Results of centrally read assessments will be available to Investigators during or after the study depending on the assessment.

9.2 SECONDARY ENDPOINT(S)

9.2.1 Efficacy endpoints

Blood levels of biomarkers of GD1 (chitotriosidase, plasma GL-1 and lyso-GL-1) will be evaluated at baseline and twice yearly. These markers will be measured in a central laboratory. Measured values as well as absolute and percent changes from study baseline and eliglustat baseline will be summarized.

9.2.2 Safety endpoints

9.2.2.1 Adverse events

Refer to [Section 10.5](#) to [10.7](#) for details.

Continuous monitoring will be performed for (S)AEs and concomitant medications.

Results of pregnancy testing for female patients of childbearing potential will be collected.

9.2.2.2 Laboratory safety variables

The clinical laboratory data consist of hematology analyses. These analyses will be conducted by local laboratories at each site. Clinical laboratory values will be analyzed after conversion into standard international units. International units will be used in all listings and tables.

9.2.2.3 Physical examination

Complete physical exam will be performed including complete neurological exam with ocular motility test.

9.2.3 Patient Reported Outcomes

Patients' quality of life (Short Form-36 Health survey) will be evaluated at baseline and twice-yearly.

The SF-36 survey is a self-reported questionnaire used to measure a patient's profile of functional health and well-being as well as psychometrically-based physical and mental health summary measures. The SF-36 is a multi-purpose, short-form health survey with 36 questions. Accordingly, the SF-36 has proven useful in surveys of general and specific populations, comparing the relative burden of diseases, and in differentiating the health benefits produced by a wide range of different treatments ([19](#)). A recall period of 1 week will be used.

9.3 PHARMACOKINETICS

Although PK samples are not scheduled, unscheduled PK samples may be collected in individual cases after discussion between the investigator and Genzyme.

9.3.1 Sampling time

Sampling times will be decided in each case after discussion between the investigator and Genzyme.

9.3.2 Pharmacokinetics handling procedure

Special procedures for collection, storage and shipping of plasma will be described in the operational manual for handling samples.

9.3.3 Bioanalytical method

Plasma Genz-99067 will be measured with a validated liquid chromatography coupled to tandem mass spectrometry method with a lower limit of quantification of 0.2 ng/mL.

9.3.4 Pharmacokinetics parameters

Not applicable.

9.4 FUTURE USE OF SAMPLES

Not all of the samples collected during this study may be required for the tests planned in this clinical trial. For subjects who have consented to it, the samples that are unused or left over after testing may be used for other research purposes (excluding genetic analysis) related to lysosomal storage disorders than those defined in the present protocol.

These other research analyses will help to understand either disease subtypes or drug response, or to develop and/or validate a bioassay method, or to identify new drug targets or biomarkers.

These samples will remain labelled with the same identifiers than the one used during the study (ie, subject ID). They will be transferred to a Sponsor site (or a subcontractor site), which can be located outside of the country where the study is conducted. Genzyme has included safeguards for protecting subject confidentiality and personal data (see [Section 14.3](#) and [Section 14.5](#)).

9.5 APPROPRIATENESS OF MEASUREMENTS

9.5.1 Primary endpoint

The primary endpoint, bone disease, will be assessed using measurements that have been validated for Gaucher disease or for other more common bone conditions.

Gaucher disease clinical assessments (mobility, bone pain and bone crisis) are established clinical parameters of bone lesions in Gaucher disease ([8](#)).

Magnetic Resonance Imaging is an established procedure to evaluate bone marrow not only for Gaucher disease, but also in oncology ([20](#)). It avoids the exposure to ionizing radiations observed with computerized tomography. A semi-quantitative method of measuring bone marrow infiltration by MRI has been developed and validated ([18](#)). It requires only standard equipment. Therefore, it can be implemented in study sites worldwide. Central reading of the images by trained readers will increase the quality and decrease the variability of the results.

Bone MRI also allows detecting lytic lesions, osteonecrosis, infarction and fractures.

Bone MRI will be performed yearly, a standard frequency in patients who are expected to be stable after multiple years of eliglustat treatment.

Dual-energy X-ray absorptiometry is the gold standard to measure BMD. A yearly frequency has been established as the time necessary to see significant changes in BMD.

Femur and spine X-Ray will serve mainly as references for additional follow up of the patients once they have left the study, when MRI may not be widely available or traditionally used to follow patients.

Bone biomarkers

Total procollagen type 1 N-terminal propeptide (P1NP), a marker of bone formation, and C-terminal telopeptide of type 1 collagen (CTX), a marker of bone resorption, have been recommended as reference markers of fracture risk assessment in age related osteoporosis by a working group of the International Osteoporosis Foundation and the International Federation of Clinical Chemistry and Laboratory Medicine (21).

MIP1 β has been shown to display moderate sensitivity and specificity to detect osteonecrosis in Gaucher disease (22).

9.5.2 Secondary endpoints

The use of patient reported outcomes as provided by quality of life questionnaires is encouraged by health authorities and entities paying for health care. In the absence of a validated tool to specifically assess disease burden in Gaucher disease type I patients, SF-36 has been selected because it is validated in multiple diseases and is available in multiple languages.

Chitotriosidase is an established biomarker in Gaucher disease and is thought to reflect the total body burden in Gaucher cells, except in patients who carry 1 or 2 null allele. Its level is related to the amount of GL-1, the substrate that accumulates as a result of the decreased activity of mutated acid β -glucuronidase. Its level is elevated in untreated patients, especially the more severely affected ones, and decreases when patients improve on ERT or SRT (see for example (23)(24).

10 STUDY PROCEDURES

10.1 GENERAL CONSIDERATIONS

Imaging:

Central reading will be set up for liver and spleen MRI and bone imaging. All imaging procedures will be performed locally and the images copied onto an electronic support and shipped to a central facility for interpretation. Interpretation by local specialists will be used for the usual care of the patients, but its results will not be entered in the clinical database.

Urine Pregnancy test:

In addition to the blood pregnancy tests performed at every visit, prior to performing any radiologic study assessment (imaging), a urine pregnancy test must be performed and the result reviewed by the radiologist/technician who will document that the patient has a negative pregnancy test result by signing, dating, and noting the time of the review on the pregnancy result report. In case of a positive pregnancy test, radiologic study assessments will not be performed.

In addition female patients must perform a urine pregnancy test at home every 4 weeks while receiving eliglustat treatment.

Any positive urine pregnancy test will be verified with a blood pregnancy test. All pregnancy tests results must be documented in the patient file.

Laboratory tests:

All laboratory tests will be done at the local laboratory at the exception of those for biomarkers, which will be done in central laboratories.

10.2 VISIT SCHEDULE

All visits will be outpatient visits. However, for patients who have to travel long distances to come to a site, overnight stay in the hospital or in a lodging facility nearby may be used.

10.2.1 Screening period

Screening will be performed between 45 and 1 day before Day 1 of the study. Screening can be performed at the time of the EOS visit of the previous study the patient was enrolled in.

Final GZGD00304, GZGD02507, GZGD02607 and GZGD03109 study assessments may serve as entry evaluation for this study if performed less than 3 month for laboratory testing, 1 year for bone imaging and 6 months for other assessments.

However, safety (S)AE, concomitant medication and prior medication history, physical examinations, HIV antibody, hepatitis C antibody, or hepatitis B surface antigen, blood pregnancy test, height will have to be performed in all cases.

Patients will be assigned a unique ID number. This new ID number as well as the number of the previous study the patient was enrolled in and his/her ID number in that study will appear in the clinical database.

For some assessments it will be possible to use results from the end of study visit of the previous eliglustat study the patient was enrolled in. For others they will need to be performed anew. See detail below.

The screening procedures do not have to be performed over 2 visits. Scheduling will be based on investigator, patient and resources availability.

After completion of all the screening assessments, the investigator will review their results to confirm that each patient meets all the inclusion criteria and none of the exclusion criteria before scheduling the patient for the Day 1 visit.

10.2.1.1 Clinical information

- Demographic data will be entered in the corresponding CRF.
- Previous medical/surgical history entered in the CRF of the previous study should not be re-entered in the Medical history CRF of this study, but will be used in the analysis of this study.
- The following categories of medico/surgical events are considered part of the medical/surgical history of the patient and should be entered in the Medical/surgical history CRF:
 - AEs started during the previous study, which are closed at the time of the screening visit and are still considered clinically significant by the investigator at the time of the screening visit.
 - Medical/surgical events started after the follow-up phone call of the previous study and before the ICF signing in the current study, whether ongoing or closed, if they are considered clinically significant by the investigator.
 - Clinically significant abnormal laboratory test results at Visits 1 and 2 (Screening period)
- AEs started during the previous study, which are ongoing at the time of the screening visit should be entered in the AE CRF regardless of whether the patient had a gap in eliglustat treatment after the end of the previous study, or the end of study visit of the previous study and the screening visit of this study are concomitant.
- Concomitant medications: Any concomitant medication the patient is taking at the time of screening or took during the previous 30 days. This should include eliglustat if the last dose of eliglustat in the previous study was taken 30 days or less prior to the screening

visit. ERT should be included if the patient was on ERT during the period between the end of the previous study and the screening visit.

- Complete physical exam including weight and height
- Gaucher disease clinical assessments
- SF-36, to be completed at the study site by the patient before any other study assessment.

10.2.1.2 Imaging

- X-Rays of both femurs and lumbar spine, unless the same exams were performed as part of the previous study 1 year or less prior.
- DXA of both hips and the lumbar spine, unless the same exams were performed as part of the previous study 1 year or less prior.
- MRI of both femurs and lumbar spine, unless the same exams were performed as part of the previous study 1 year or less prior,
- Spleen and liver MRI, unless the same exams were performed as part of the previous study 6 months or less prior.

Details on technical specifications and quality control for these procedures will be provided in the vendor manual and must be strictly followed.

10.2.1.3 Laboratory tests

To be collected only if there were performed more than 3 months ago as part of the previous study the patient was enrolled in and the results are available, except for the viral serologies and the blood pregnancy test (only for female of child bearing potential), which will need to be performed in all cases.

- Viral serologies: human immunodeficiency virus antibody, and hepatitis C antibody or hepatitis B surface antigen.
- Complete blood count (hemoglobin, hematocrit, red blood cell count, white blood cell count and differential, platelet count, red blood cell parameters, reticulocytes)
- Liver functions tests: AST, ALT, Alkaline phosphatase (AP), total bilirubin, albumin, GGT.
- Biomarkers: serum chitotriosidase; plasma MIP1- β ; serum P1NP; serum CTX that must be collected after overnight fasting; plasma GL-1; plasma lyso-GL-1.
- For women of child bearing potential: blood pregnancy test.

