WEEKS			Da y 1	Wk 26 (±14 days)	Wk 52 (±14 days)	Wk 78 (±14 days)	Wk 104 (±14 days)	Wk 130 (±14 days)	Wk 156 (±14 days)	Wk 182 (±14 days)	Wk 208 (±14 days)	Every 6 months (±14 days)	Every 12 Months (±14 days)	Every 24 months (±14 days)		
Human immunodeficiency virus (HIV) antibody, Hepatitis C antibody, or Hepatitis B surface antigen.	X															
Hematology (including hemoglobin, platelet)	X			X	X	X	X	X	X	X	X	X	X	X	X	X
Serum Chemistry (AST, ALT, AP, Total bilirubin, albumin, GGT)	X															
Biomarkers: serum chitotriosidase, plasma MIP- 1 β , serum P1NP, serum CTX ^h , plasma GL-1 and lyso-GL-1	X			X	X	X	X	X	X	X	X	X	X	X		X
Blood pregnancy test (for women of childbearing potential) ⁱ	X	X	X	X	X	X	X	X	X	X	X	X	X	X		X

	Screening (Day -45 to -1) ^a		Treatment Observations													Study completion or Patient Discontinuation/Withdrawal ^b	
			1	2	3	4	5	6	7	8	9	10	11	Assessments after Week 208			
WEEKS			Da y 1	Wk 26 (±14 days)	Wk 52 (±14 days)	Wk 78 (±14 days)	Wk 104 (±14 days)	Wk 130 (±14 days)	Wk 156 (±14 days)	Wk 182 (±14 days)	Wk 208 (±14 days)	Every 6 months (±14 days)	Every 12 Months (±14 days)	Every 24 months (±14 days)			

^a Final GZGD00304, GZGD02507, GZGD02607 and GZGD03109 study assessments may serve as entry evaluation for this study if performed less than 3 month for laboratory testing, 1 year for bone imaging (X-ray femur and lumbar spine, dual-energy X-ray absorptiometry (DXA) hips and lumbar spine, Magnetic Resonance Imaging (MRI) femur and lumbar spine) and 6 months for other assessments. However, safety (S)AE, concomitant medication and prior medication history, physical examinations, human immunodeficiency virus (HIV) antibody, hepatitis C antibody, or hepatitis B surface antigen, blood pregnancy test for female of childbearing potential, height, will have to be performed in all cases. The screening procedures do not have to be performed over 2 visits. Scheduling will be based on investigator, patient and resources availability. Screening can be performed at the same time as the end-of-study visit of the previous study the patient was enrolled in.

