## 2.4 STATISTICAL METHODS

Analysis will be performed on safety and efficacy endpoints at 2 points in this study:

- After the last patient enrolled has completed 2 years of treatment (two-year analysis period)
- At the study completion

Both efficacy and safety results will be calculated both in reference to study entry (study period) and to first eliglustat treatment (eliglustat treatment period). Because patients will enter this study having been treated with eliglustat for various durations, two baselines will be used:

- Study baseline, defined as status at study entry, which is the last non-missing value before the first dose of eliglustat of this study; and
- Eliglustat baseline, defined as status at first dose of eliglustat in the previous Phase 2 or Phase 3 studies. The definition of eliglustat baseline should be the last non-missing value prior to first dose of eliglustat in prior studies.

The eliglustat baseline can only be obtained if the assessments in EFC13781 study and the previous studies are comparable. Assessment method, location, parameters, result evaluation, etc should be considered for comparability check if applicable. In addition, eliglustat baseline definition of hemoglobin and platelet for Phase 2 and ENCORE study were defined separately in [Section 2.5.2](#).

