#### **2.4.4.1.5 Bone biomarkers**

Absolute values, change and percent change from baseline (study baseline and eliglustat baseline) for levels of P1NP, CTx and MIP 1  $\beta$  will be summarized by visit.

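### Protocol 10.2.1.3, read literally, omits the entry blood sample when the previous-study result is unavailable or the test was never done, so some patients may lack a study baseline for the biomarkers

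*Protocol*

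**What the plan says.** Protocol 10.2.1.3 lists the screening blood tests: complete blood count, liver tests, and six biomarkers (P1NP, CTX, MIP-1β, chitotriosidase, GL-1, lyso-GL-1). Its opening sentence makes their collection conditional, in an only-if form: "if there were performed more than 3 months ago as part of the previous study the patient was enrolled in and the results are available". Only the serologies and the pregnancy test escape the condition.

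Other parts of the protocol set a different default:

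- The flow chart (1.2) marks these tests at screening. Its footnote a says that final assessments from the previous study "may serve as entry evaluation for this study if performed less than 3 month for laboratory testing".
- Section 10.2.1 repeats that permission. It adds, of assessments that cannot be carried over, "For others they will need to be performed anew. See detail below". For blood tests, the detail below is 10.2.1.3.
- Sections 9.1.5 and 9.2.1 call for the bone and GD1 biomarkers at baseline, without condition.
- Section 10.2.1.2, on imaging, uses the unless form: the scan is done unless a sufficiently recent one exists.
- Section 10.2.2 (Day 1) lists a physical examination and a pregnancy test, and no other blood sample.

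In the SAP, section 2.4 defines study baseline as the status at entry, "which is the last non-missing value before the first dose of eliglustat of this study". Table 2 (section 2.5.4) gives the baseline window as Day -45 to Day 1, and its Schedule C applies that window to biomarkers and hematology. Section 2.4.4.1.5 plans "Absolute values, change and percent change from baseline (study baseline and eliglustat baseline) for levels of P1NP, CTx" and MIP-1β. Protocol 11.4 and SAP 2.4.4 rule out imputation.

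**The concern.** Availability of an old result makes sense as a reason not to draw a new sample. In 10.2.1.3 it has become a requirement for drawing one. The only-if form also makes a previous test a precondition for the new one, so a patient who never had the test is not sampled.

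P1NP, CTX and MIP-1β make up one of the five primary skeletal domains, and the other three markers are the secondary efficacy endpoints. All six are summarised as change from study baseline. A skipped screening sample cannot be made good before dosing, because the next scheduled draw is Week 26. If the marker was also never measured in the previous study, the eliglustat baseline is missing too, and the entry sample is the only possible reference value.

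**Working it through.** The documents give no figure to reproduce here; Protocol 11.1 states that no sample size calculation was made. The check compares two collection rules.

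**Inputs**

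- Literal rule (10.2.1.3): draw only if the test was done in the previous study AND more than 3 months ago AND the result is available.
- General rule (10.2.1 and footnote a): draw unless a test less than 3 months old stands in. I assume that a result must be in hand to stand in; those passages state only the age condition.

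| Previous-study test | 10.2.1.3 as written | 10.2.1 and footnote a | Agree? |
|---|---|---|---|
| Under 3 months, available | no draw | no draw | yes |
| Under 3 months, unavailable | no draw | draw (on the assumption above) | no |
| Over 3 months, available | draw | draw | yes |
| Over 3 months, unavailable | no draw | draw | no |
| Never done | no draw | draw | no |

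The rules disagree in 3 of 5 situations, or in 2 of 5 if the age condition alone decides and the second row is counted as agreement. These are counts of logical situations and say nothing about how often each occurs. Under the general rule with the assumption, the sample is drawn in 4 of 5 situations, against 1 of 5 as written.

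**Consequence for one affected patient**

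- Biomarker visits after baseline: Weeks 26, 52, 78 and 104, so 4 to the two-year analysis and 8 to Week 208.
- Change-from-study-baseline values at risk: up to 6 markers × 4 visits = 24 to Week 104, or 6 × 8 = 48 to Week 208.
- Share of the planned sample: 1/32 = 3.1%.

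**What the SAP would then do**

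- Never measured: there is no pre-dose value, so change from study baseline is missing.
- Latest result unavailable but an older one on file: the last-non-missing rule in 2.4 would take the older value, while the Table 2 window would exclude it if it predates Day -45. The two SAP rules give different answers.

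The same SAP conflict reaches values that the protocol accepts. Three months is about 365.25/4 = 91 days. If the limit runs back from Day 1, an accepted value between 46 and about 91 days old falls outside the Table 2 window. If it runs back from a screening visit on Day -45, an accepted value could date from about 45 + 91 = 136 days before Day 1. The protocol does not say which date the limit is counted from.

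**The case against.** The strongest reply is that this is one garbled clause surrounded by clear text. The flow chart schedules the tests, 9.1.5 and 9.2.1 require a baseline value, 10.2.1 says that what cannot be carried over is done anew, and the imaging list shows the intended form. Most sites would draw the sample. The study is descriptive, with no hypothesis tests and no composite endpoint. An affected patient stays in the full analysis set, in the summaries of measured values and, where data exist, in change from eliglustat baseline.

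Much of this stands, and it rules out several stronger readings that a reader might infer:

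- *The rule is reversed altogether.* It is not. With an available result, an old test leads to a new sample and a recent one does not, as intended.
- *These patients have no valid study baseline.* That follows only where a site puts 10.2.1.3 above the other sections.
- *The liver criterion E 04 goes unchecked.* Liver tests are scheduled only at screening and fall under the same sentence. However, E 04 asks for current enzymes, and 10.2.1 has the investigator review all screening results against the criteria before Day 1 is scheduled. That review largely protects the check.
- *The SAP puts no age limit on the baseline value.* Section 2.4 has none, but Table 2 does.
- *P1NP and CTX were not measured in the previous studies.* The Protocol introduction reports MIP-1β results from GZGD02507 and GZGD03109 and none for P1NP or CTX. Not being reported there does not show that they were not measured, and the SAP's planned change from eliglustat baseline presupposes some earlier data.

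The reply does not dispose of the point, because 10.2.1 sends the site to the detail below, and for blood tests that detail is the faulty sentence. A sample omitted for this reason is lost for good.

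**Conclusion.** The point holds as a certain contradiction with a conditional effect. The opening sentence of 10.2.1.3 gives a wrong instruction when the previous-study result is unavailable or the test was never done. Where a site follows it, the patient may lack a study baseline for the bone and GD1 biomarkers and leave the change-from-study-baseline summaries for them.

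The size cannot be fixed from the documents. They do not say how many of the approximately 32 patients lack an available result, or which markers each previous study measured. The number affected could be zero. If a marker was not measured in one of the previous studies (an assumption), every patient from that study would depend on the entry sample for that marker.

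The SAP's two baseline rules need reconciling in any case, because they also disagree about some values that the protocol accepts.

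**What to change.** **Protocol 10.2.1.3.** Replace the opening sentence with: *To be collected at screening unless the same test was performed in the previous study less than 3 months earlier and its result is available; viral serologies and the blood pregnancy test (women of childbearing potential) are performed in all cases.* State the date from which the 3 months is counted.

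**SAP 2.4 and Table 2.** Reconcile the last-non-missing definition with the Day -45 to Day 1 window, so that a previous-study laboratory value accepted by the protocol (up to 3 months old) counts as study baseline and an older one does not. Adding a 3-month limit beside the existing window would leave two competing limits, so the window itself must be adjusted for these values.

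**Cost.** One protocol sentence and a short SAP edit. No procedure is added, because the flow chart already schedules the sample. A few patients may have blood drawn that the literal text would have skipped.
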